7.1 Interim Analysis and Early Stopping Guidelines

7.1.1 Phase 1 (Part 1 - Dose Exploration)

Safety data will be reviewed on an ongoing basis by Amgen. Based on accumulating toxicity information, BLRM will be used to make dosing recommendations based on the DLT Evaluable Set. In DLRMs, Amgen, in consultation with DLRT, will review the BLRM recommended dose level and will review all available cumulative data by cohort prior to making dose escalation decisions. As a sensitivity analysis, a one-parameter Continual Reassessment Method (CRM) model may be used to estimate the dose-toxicity relationship to help make dose escalation decisions. Adverse events and DLTs observed in all subjects (including backfill subjects) will be evaluated continually and fully integrated into all DLRMs and considered in all enrollment and dosing decisions.

The DLRT members, quorum, voting members, and recommendations are described in Protocol Section 10.4.1.1.

7.1.2 Phase 1 (Part 2 – Dose Expansion)

This same DLRT will be responsible for reviewing data in the dose expansion phase to confirm the RP2D and determine the benefit/risk of proceeding to the phase 2 part of the study. The dose expansion part of the study (phase 1 - part 2) can open once an MTD or a RP2D and dosing schedule has been estimated in the dose exploration part of the study (phase 1 – part 1). If no DLT is observed in phase 1 – part 1, the RP2D will be estimated based on composite review of PK, overall safety/tolerability, and observed responses. Further confirmation of the RP2D dose will be sought in the phase 1 part 2 dose expansion.

In the dose expansion, additional subjects will be enrolled at the RP2D estimated in the phase 1 part 1 dose exploration. After a minimum of 20 subjects have been enrolled to the initial estimated monotherapy RP2D (including subjects enrolled to the RP2D in either the dose exploration [approximately 6] or the dose expansion [approximately 14] parts of the study) and have completed the 21-day DLT period, and after a minimum of 10 of these subjects have at least 6 weeks of response data (including all previous data from the dose expansion and backfill cohorts), the DLRT will review all available safety, laboratory, PK, and efficacy (physician assessment) data.

After the first review has been conducted, if a decision is made to continue to obtain additional data at the initial estimated RP2D prior to proceeding to phase 2, the intervals for subsequent reviews will be determined by the DLRT but should occur within a maximum of 20 additional subjects enrolled and dosed for 21 days. The maximum number of subjects that may be enrolled to the initial estimated RP2D in the monotherapy dose expansion group, without confirmation of this dose for phase 2, will not exceed 60. If another dose (or schedule) needs to be explored, additional subjects on that dose (or schedule), up to a total of 60, may be enrolled.

Based on emerging clinical efficacy data, the number of subjects with specific tumor types may be restricted/specified in the expansion part.

Antitumor activity will be monitored in terms of ORR by tumor types (NSCLC, CRC). Futility and efficacy thresholds will be calculated using Bayesian posterior probability approach based on the cumulative efficacy data and it will serve as a guidance to the DLRT. Enrollment will not be held to conduct this assessment.

Whenever DLRT will review the data, and there are at least 5 evaluable subjects in the tumor type, the futility and efficacy thresholds for that tumor type will be calculated using

all the cumulative efficacy data in phase 1 Monotherapy RP2D ORR Analysis Set to provide the guidance. In the calculation of thresholds, a response is defined as either a confirmed or unconfirmed CR or PR as per RECIST 1.1.

7.1.2.1 Futility Thresholds

For NSCLC, the futility thresholds are calculated such that the Bayesian posterior probability of a true $ORR \leq 0.15$ is $>$ a high probability of 75%. For CRC, the futility thresholds are calculated such that the Bayesian posterior probability of a true $ORR \leq 0.05$ is $>$ than a high probability of 75%. A noninformative prior distribution of beta (1, 1) will be used.

NSCLC: probability ($ORR \leq 0.15$) $>$ 75%

CRC: probability ($ORR \leq 0.05$) $>$ 75%

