10.4.1.2.1 Futility Thresholds

For NSCLC, the futility thresholds are calculated such that the Bayesian posterior probability of a true ORR ≤ 0.15 is $>$ a high probability of 75%. For CRC, the futility thresholds are calculated such that the Bayesian posterior probability of a true ORR ≤ 0.05 is $>$ than a high probability of 75%. A noninformative prior distribution of beta (1, 1) will be used.

NSCLC: probability (ORR ≤ 0.15) $>$ 75%

CRC: probability (ORR ≤ 0.05) $>$ 75%

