7.1.2.2 Efficacy Thresholds

For NSCLC, the efficacy thresholds are calculated such that the Bayesian posterior probability of a true $ORR > 0.25$ is \geq to a high probability of 60%. For CRC, the efficacy thresholds are calculated such that the Bayesian posterior probability of a true $ORR > 0.1$ is \geq to a high probability of 60%. A noninformative prior distribution of beta (1, 1) will be used.

NSCLC: probability [$ORR > 0.25$] \geq 60%

CRC: probability [$ORR > 0.1$] \geq 60%

[Table 2](#) and [Table 3](#) are look up tables calculated for NSCLC and CRC, providing the detailed futility and efficacy thresholds with different numbers of response-evaluable subjects (having at least 6-week response data) when DLRT review the data. For example, at the time when DLRT plan to review the data, there are a total of 25 response-evaluable NSCLC subjects. If observing number of the response is ≤ 2 , based on the table, the guidance will recommend not to continue due to the lack of efficacy. If observing number of the response is ≥ 7 , the guidance will recommend continuing to phase 2. If the observing number of the response is in between and the total number of response-evaluable subjects at that RP2D has not reached the maximum 60, the guidance will recommend enrolling more patients in the phase 1 expansion cohort.

The operating characteristics of these thresholds are demonstrated assuming a minimal of 5 response-evaluable subjects per tumor type for the first DLRT review and

every 5 response-evaluable subjects thereafter. The actual sample size per tumor type at each look will depend on tumor type distribution. Table 4 and Table 5 show the cumulative probabilities of recommending DLRT to stop the trial due to lack of efficacy and the cumulative probabilities of recommending DLRT to continue to phase 2 given the true ORR ranging from 0.1 to 0.5 for NSCLC subjects and 0.05 to 0.25 for CRC subjects.

Table 2. Look Up Table for NSCLC Subjects

Number of Subjects	Recommend Not to Continue if Observing the Number of Responses Below
5 ~ 7	Never stop for futility with this number of subjects
8 ~ 16	0
17 ~ 24	≤ 1
25 ~ 31	≤ 2
32 ~ 39	≤ 3
40 ~ 47	≤ 4
48 ~ 54	≤ 5
55 ~ 60	≤ 6
Number of Subjects	Recommend Go to Phase 2 if Observing the Number of Responses below
5 ~ 8	≥ 2
9 ~ 11	≥ 3
12 ~ 15	≥ 4
16 ~ 19	≥ 5
20 ~ 23	≥ 6
24 ~ 26	≥ 7
27 ~ 30	≥ 8
31 ~ 34	≥ 9
35 ~ 38	≥ 10
39 ~ 42	≥ 11
43 ~ 46	≥ 12
47 ~ 50	≥ 13
51 ~ 54	≥ 14
55 ~ 57	≥ 15
58 ~ 60	≥ 16

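### The CRC phase 1 futility look-up table changes one subject late: under the stated rule, 1 response in 52 already qualifies, but the table starts that row at 53

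*Supplement*

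**What the plan says.** SAP Section 7.1.2.1 sets the rule in words: "For CRC, the futility thresholds are calculated such that the Bayesian posterior probability of a true" ORR of 0.05 or less is greater than 75%. The inequality is strict, no rounding convention is given, and "A noninformative prior distribution of beta (1, 1) will be used". Protocol Amendment 3, Section 10.4.1.2.1, states the same rule and prior.

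The rule is turned into counts in SAP Table 3 and, identically, in protocol Table 11. The CRC futility rows are:

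- 5 to 26 subjects: never stop for futility
- 27 to 52 subjects: 0 responses
- 53 to 60 subjects: at most 1 response

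The Go threshold in the same tables is at least 6 responses for 50 to 59 subjects. When the count lies between the two thresholds and the maximum of 60 evaluable subjects at that dose has not been reached, the "guidance will recommend enrolling more patients in the phase 1 expansion cohort" (SAP Section 7.1.2.2). SAP Section 7.1.2 says of the thresholds that "it will serve as a guidance to the DLRT".

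**The concern.** The look-up table exists to give the integer cut-offs that follow from the posterior rule, so a reader expects the two to agree at every sample size. They do not agree at 52 evaluable CRC subjects with 1 response. Someone reading the table would report a result in the middle zone, and someone computing the posterior from the stated rule would report futility. Review sizes are not fixed in advance: the DLRT sets its own intervals, and the number of subjects per tumour type at each look depends on the tumour mix. A look at 52 is therefore possible, though unlikely.

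**Working it through.** **Inputs.** Cut-off 0.05, required probability above 0.75, and prior beta(1,1), all from SAP Section 7.1.2.1. Row boundaries are from SAP Table 3.

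**Formula.** With x responses in n subjects the posterior is Beta(1 + x, 1 + n − x).

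- For x = 0: P(ORR ≤ 0.05) = 1 − 0.95^(n+1)
- For x = 1: P(ORR ≤ 0.05) = 1 − 0.95^(n+1) − (n+1) × 0.05 × 0.95^n

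**Reproducing the table's first boundary (x = 0).**

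- n = 26: 0.749656, not above 0.75
- n = 27: 0.762173, above 0.75

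The row for 0 responses therefore starts at 27, as printed. This confirms that the prior, the cut-off and the direction of the inequality are read correctly.

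**The second boundary (x = 1).**

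- n = 51: 1 − 0.0694428 − 52 × 0.05 × 0.0730977 = 1 − 0.0694428 − 0.1900541 = 0.740503
- n = 52: 1 − 0.0659707 − 53 × 0.05 × 0.0694428 = 1 − 0.0659707 − 0.1840235 = 0.7500058
- n = 53: 1 − 0.0626722 − 54 × 0.05 × 0.0659707 = 1 − 0.0626722 − 0.1781209 = 0.759207

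The first n at which 1 response satisfies the rule is 52. The table gives 53.

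**All other boundaries.** The four blocks (NSCLC and CRC, futility and Go) were rebuilt for n = 5 to 60, which is 4 × 56 = 224 cells. The only difference from SAP Tables 2 and 3 is CRC futility at n = 52.

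**Another prior?** A Beta(0.5, 0.5) prior would put the two CRC changes at 13 and 41. A Beta(0.05, 0.95) prior would put the starts of the at-most-1 and at-most-2 rows at 29 and 55. Neither reproduces the printed table.

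**Rounding?** In SAP Table 2, 3 NSCLC responses in 32 count as futile. The posterior there is Beta(4, 30), and P(ORR ≤ 0.15) = 0.750455.

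- Rounded to three decimals or to a whole percent, that value is not above 75%, and the NSCLC row could not start at 32.
- Rounded to five or more decimals, the CRC value stays above 75%.
- Rounded to four decimals, the values are 0.7505 and 0.7500, which reproduces both tables.

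**Operating characteristics.** SAP Table 5 assumes a first look at 5 subjects and looks "every 5 response-evaluable subjects thereafter", so the looks nearest 52 are at 50 and 55. With a true ORR of 0.05, the recomputed cumulative No Go probability is 21.5% at 50 and 27.7% at 55, against 21% and 28% printed. The 50-subject figure is 0.95^30 = 21.46% before rounding. Moving the row start to 52 changes none of these.

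**The case against.** The strongest defence is that the excess over the cut-off is 0.0000058. To four decimals the posterior is 0.7500, which is not greater than 75%, so the table may only reflect ordinary printed precision. This cannot be excluded. However, the documents state no such convention, and the NSCLC table rules out coarser rounding.

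The second defence is that nothing turns on it, and most of that stands:

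- The thresholds are guidance, and the decision to proceed rests on the totality of the data.
- They are also to be calculated whenever the DLRT reviews data, so the table is not the only route to them.
- Enrolment is not held for the assessment.
- At 53 subjects with 1 response, rule and table agree again.
- The advice to enrol more applies only while fewer than 60 subjects are evaluable at that dose. If that cap counts all tumour types, 52 CRC subjects leave room for at most 59 − 52 = 7 others. That is far from the mixed-tumour expansion described.

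A reader might infer that table and rule give opposite guidance. They do not: at 1 response in 52 the table does not recommend Go, which needs at least 6. The disagreement is between not continuing and enrolling more, one step apart.

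**Conclusion.** The point holds as a small inconsistency. As written, the rule gives 0 responses for 27 to 51 subjects and at most 1 for 52 to 60. SAP Table 3 and protocol Table 11 change one subject later. One cell in 224 is affected, by 0.0006 percentage points, in non-binding guidance.

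This rests on applying the rule literally and unrounded with the beta(1,1) prior. A stated four-decimal convention would remove the mismatch. It would be wrong to infer a faulty method or misstated operating characteristics: every other boundary reproduces, and SAP Table 5 and protocol Table 13 have no look at 52. The documents do not say why the cell differs. Lowest severity.

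**What to change.** In SAP Table 3 and protocol Table 11, change the CRC futility rows to 27 ~ 51 with 0 responses and 52 ~ 60 with at most 1 response, so that the table matches the rule. This costs two cells in each document. No rule, sample size or operating characteristic has to be recalculated. If the sponsor did intend to evaluate the probability to four decimals, one sentence saying so next to the rule would reconcile rule and table instead.

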7.1.2.2 Efficacy Thresholds

For NSCLC, the efficacy thresholds are calculated such that the Bayesian posterior probability of a true $ORR > 0.25$ is \geq to a high probability of 60%. For CRC, the efficacy thresholds are calculated such that the Bayesian posterior probability of a true $ORR > 0.1$ is \geq to a high probability of 60%. A noninformative prior distribution of beta (1, 1) will be used.

NSCLC: probability [$ORR > 0.25$] \geq 60%

CRC: probability [$ORR > 0.1$] \geq 60%

[Table 2](#) and [Table 3](#) are look up tables calculated for NSCLC and CRC, providing the detailed futility and efficacy thresholds with different numbers of response-evaluable subjects (having at least 6-week response data) when DLRT review the data. For example, at the time when DLRT plan to review the data, there are a total of 25 response-evaluable NSCLC subjects. If observing number of the response is ≤ 2 , based on the table, the guidance will recommend not to continue due to the lack of efficacy. If observing number of the response is ≥ 7 , the guidance will recommend continuing to phase 2. If the observing number of the response is in between and the total number of response-evaluable subjects at that RP2D has not reached the maximum 60, the guidance will recommend enrolling more patients in the phase 1 expansion cohort.

The operating characteristics of these thresholds are demonstrated assuming a minimal of 5 response-evaluable subjects per tumor type for the first DLRT review and

every 5 response-evaluable subjects thereafter. The actual sample size per tumor type at each look will depend on tumor type distribution. Table 4 and Table 5 show the cumulative probabilities of recommending DLRT to stop the trial due to lack of efficacy and the cumulative probabilities of recommending DLRT to continue to phase 2 given the true ORR ranging from 0.1 to 0.5 for NSCLC subjects and 0.05 to 0.25 for CRC subjects.

Table 2. Look Up Table for NSCLC Subjects

Number of Subjects	Recommend Not to Continue if Observing the Number of Responses Below
5 ~ 7	Never stop for futility with this number of subjects
8 ~ 16	0
17 ~ 24	≤ 1
25 ~ 31	≤ 2
32 ~ 39	≤ 3
40 ~ 47	≤ 4
48 ~ 54	≤ 5
55 ~ 60	≤ 6
Number of Subjects	Recommend Go to Phase 2 if Observing the Number of Responses below
5 ~ 8	≥ 2
9 ~ 11	≥ 3
12 ~ 15	≥ 4
16 ~ 19	≥ 5
20 ~ 23	≥ 6
24 ~ 26	≥ 7
27 ~ 30	≥ 8
31 ~ 34	≥ 9
35 ~ 38	≥ 10
39 ~ 42	≥ 11
43 ~ 46	≥ 12
47 ~ 50	≥ 13
51 ~ 54	≥ 14
55 ~ 57	≥ 15
58 ~ 60	≥ 16

NSCLC = non-small cell lung carcinoma

Table 3. Look Up Table for CRC Subjects

Number of Subjects	Recommend Not to Continue if Observing the Number of Responses Below
5 ~ 26	Never stop for futility with this number of subjects
27 ~ 52	0
53 ~ 60	≤ 1
Number of Subjects	Recommend Go to Phase 2 if Observing the Number of Responses Below
5 ~ 12	≥ 1
13 ~ 21	≥ 2
22 ~ 31	≥ 3
32 ~ 40	≥ 4
41 ~ 49	≥ 5
50 ~ 59	≥ 6
60	≥ 7

CRC = colorectal cancer

Table 4. Cumulative Probability of Go/No Go for NSCLC Subjects

Number of Subjects	True ORR					
	0.1		0.3		0.5	
	No Go	Go	No Go	Go	No Go	Go
5	0%	8%	0%	47%	0%	81%
10	35%	11%	3%	67%	0%	96%
15	35%	13%	3%	77%	0%	99%
20	48%	13%	3%	79%	0%	99%
25	60%	13%	4%	83%	0%	100%
30	60%	13%	4%	85%	0%	100%
35	65%	13%	4%	86%	0%	100%
40	70%	13%	4%	87%	0%	100%
45	70%	13%	4%	89%	0%	100%
50	73%	13%	4%	90%	0%	100%
55	76%	13%	4%	90%	0%	100%
60	76%	13%	4%	91%	0%	100%

ORR = objective response rate.

Numbers are for demonstration purpose. The actual sample size per tumor type at each look will depend on tumor type distribution

Table 5. Cumulative Probability of Go/No Go for CRC Subjects

Number of Subjects	True ORR					
	0.05		0.15		0.25	
	No Go	Go	No Go	Go	No Go	Go
5	0%	23%	0%	56%	0%	76%
10	0%	40%	0%	80%	0%	94%
15	0%	41%	0%	84%	0%	96%
20	0%	45%	0%	89%	0%	99%
25	0%	46%	0%	91%	0%	99%
30	21%	47%	1%	93%	0%	100%
35	21%	48%	1%	94%	0%	100%
40	21%	48%	1%	95%	0%	100%
45	21%	48%	1%	96%	0%	100%
50	21%	48%	1%	96%	0%	100%
55	28%	49%	1%	96%	0%	100%
60	28%	49%	1%	96%	0%	100%

ORR = objective response rate.

Numbers are for demonstration purpose. The actual sample size per tumor type at each look will depend on tumor type distribution.

Based on emerging clinical efficacy data, the number of subjects with specific tumor types may be restricted/specified in the expansion part.

The DLRT may also recommend that additional subjects be enrolled at this estimated monotherapy RP2D or that a dose reduction or alternate dosing regimen be explored before proceeding to phase 2. The decision to proceed to the phase 2 monotherapy will be based on the totality of data from both exploration and expansion parts of the study.

A final estimate of the MTD and/or RP2D using BLRM will be evaluated and confirmed utilizing all DLT-evaluable subjects from the dose exploration and the dose expansion cohorts.

7.1.3 Phase 2

7.1.3.1 Safety

A data review team (DRT), internal to Amgen but external to the study team, will assess safety after approximately 30, 50, 70, and 100 subjects have been treated for 21 days. Based on their reviews, the DRT will make recommendations to Amgen regarding the continuation of the study. There will be no formal guidelines to stop for safety. The DRT will consist of 3 or more members including 2 or more clinicians with relevant specialties

and 1 or more statisticians. The DRT will be supported by an independent statistician who is responsible for preparing reports that describe the ongoing clinical study data. Details regarding the responsibilities of the DRT and the independent statistician will be described in the DRT Charter.

7.1.3.2 Futility

The DRT will also oversee futility analyses performed by tumor type and based on the phase 2 ORR analysis set. The interim futility analyses will be conducted in a continuous manner using Bayesian predictive probability (Lee and Liu, 2008) for NSCLC and CRC separately. Interim futility analysis will be performed by tumor types (NSCLC, CRC). For NSCLC subjects, it will begin after approximately 25 response-evaluable subjects, defined as received at least 1 dose of AMG 510 and have had at least 6 weeks response data starting from day 1. For CRC subjects, it will begin after approximately 20 response-evaluable subjects. Subjects who stopped disease assessments prior to 6 weeks will be included in this analysis if the data cutoff is at least 6 weeks after their first dose date. Following this initial interim analysis, for each tumor type, subsequent interim analyses will be performed after every 10 subjects in each tumor type becomes response evaluable.

The Go criterion will be met if the probability that the true ORR exceeds the benchmark ORR is \geq to a high probability of:

Go Criterion for NSCLC: probability [ORR > 0.23] \geq 80%

Go Criterion for CRC: probability [ORR > 0.1] \geq 95%

Given the existing observed data during the continuous monitoring stage, the Bayesian predictive probability is obtained by calculating the probability of reaching a Go Criterion should the treatment group be enrolled and evaluated to the maximum planned final sample size of 105 NSCLC subjects and 60 CRC subjects. The Go criterion is for interim futility analysis purpose only.

Futility will be met if it is predicted that there is a small probability of reaching a Go Criterion upon full enrollment of 105 NSCLC subjects and 60 CRC subjects given the existing observed data. A noninformative prior distribution of beta (1, 1) will be used.

Futility NSCLS: Predictive probability of a Go decision < 5%

Futility CRC: Predictive probability of a Go decision < 30%

Further enrollment may be terminated if futility is met. The futility analyses will be based on site-assessed disease response and the futility rules will be nonbinding. Due to the efficacy already observed in NSCLC during dose escalation phase, there will be no enrollment pause for NSCLC during the futility analyses. Enrollment will be paused for CRC at the first interim futility analysis and may be paused at the subsequent interim analyses upon DRT's recommendation.

The decision rule and operating characteristics for continuous monitoring of ORR in NSCLC subjects and CRC subjects are provided in [Table 6](#) and [Table 7](#), respectively. For example, observing 3 or fewer observed responders after 25 NSCLC subjects have become evaluable would be considered futile due to a small probability of reaching a Go Criterion upon full enrollment of 105 subjects given the existing observed data.

Table 6. Stopping Boundary and Operating Characteristics in NSCLC Subjects

Number of Subjects	Considered Futile If Observing Number of Responses	Cumulative Probability of Futility					
		True ORR=0.1	True ORR=0.2	True ORR=0.3	True ORR=0.4	True ORR=0.5	True ORR=0.6
25	≤ 3	76%	23%	3%	0.2%	0.0%	0.0%
35	≤ 5	89%	32%	4%	0.3%	0.0%	0.0%
45	≤ 7	94%	39%	5%	0.3%	0.0%	0.0%
55	≤ 10	98%	51%	6%	0.3%	0.0%	0.0%
65	≤ 13	100%	63%	8%	0.3%	0.0%	0.0%
75	≤ 16	100%	73%	10%	0.3%	0.0%	0.0%
85	≤ 19	100%	80%	12%	0.4%	0.0%	0.0%
95	≤ 22	100%	85%	14%	0.4%	0.0%	0.0%
105	≤ 27	100%	94%	23%	0.5%	0.0%	0.0%
Average Number of Subjects		29	60	99	105	105	105

NSCLC = non-small cell lung carcinoma; ORR = objective response rate

Table 7. Stopping Boundary and Operating Characteristics in CRC Subjects

Number of Subjects	Considered Futile If Observing Number of Responses	Cumulative Probability of Futility					
		True ORR=0.05	True ORR=0.1	True ORR=0.15	True ORR=0.2	True ORR=0.25	True ORR=0.3
20	≤ 2	92%	68%	41%	20%	9%	4%
30	≤ 3	96%	75%	45%	23%	10%	4%
40	≤ 5	99%	85%	55%	27%	11%	4%
50	≤ 7	100%	92%	63%	32%	12%	4%
60	≤ 9	100%	95%	70%	35%	13%	4%
Average Number of Subjects		21	28	40	50	56	58

CRC = colorectal cancer; ORR = objective response rate

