The ORR will be reported by tumor types. For NSCLC, with 60 subjects, 95% of the times the true ORR will be between 0.188 and 0.432, when the observed ORR is 0.3; and when the true ORR is 0.3, the chance that the 95% CIs of ORR will be > 0.15 is 76%. For CRC, with 60 subjects, 95% of the times the true ORR will be between 0.108 and 0.323, when the observed ORR is 0.2; and when the true ORR is 0.2, the chance that the 95% CIs of ORR will be > 0.05 is 93%. Below table describes the scenarios with sample size of 20 to 60.

Table 9. Sample Size Justification

NSCLC		
Sample Size	95% Exact CI of the True ORR Given an Observed ORR = 0.3	Probability (ORR 95% CI Lower Bound > 0.15) Given True ORR = 0.3)
20	(0.119, 0.543)	39%
30	(0.147, 0.494)	41%
40	(0.166, 0.465)	56%
50	(0.179, 0.446)	67%
60	(0.188, 0.432)	76%
CRC		
Sample Size	95% Exact CI of the True ORR Given an Observed ORR = 0.2	Probability (ORR 95% CI Lower Bound > 0.05) given true ORR = 0.2)
20	(0.057, 0.437)	59%
30	(0.077, 0.386)	75%
40	(0.091, 0.356)	84%
50	(0.100, 0.337)	90%
60	(0.108, 0.323)	93%

ORR = objective response rate

[REDACTED]

Approved

10.2.2 Phase 2

The phase 2 part of the study will target an ORR over a benchmark rate to exclude based on the lower limit of the 95% CI for the observed ORR for each tumor type (NSCLC, CRC).

For NSCLC subjects, a large phase 3 trial (REVEL) for second-line treatment after disease progression on platinum-based therapy showed that an ORR of 23% was observed with ramucirumab plus docetaxel (Garon et al 2014, NCT01168973).

For CRC subjects, although the treatment for ≥ third line subjects with Regorafenib or TAS 102 has demonstrated ORR of only 1% to 4% (Li et al, 2015; Mayer et al, 2015; Grothey et al, 2013), these therapies has demonstrated survival

benefits. To justify the use of surrogate endpoint ORR in this phase 2 trial, a higher benchmark ORR for CRC is selected.

The benchmark ORR to exclude is selected as 23% for NSCLC and 10% for CRC. No benchmark ORR will be set for tumor types other than NSCLC and CRC because of low expected enrollment. A sample size of 105 subjects for NSCLC and 60 subjects for CRC will provide approximately a 90% probability that the lower limit of the ORR 95% CI exceeds the tumor-specific benchmark ORR.

The minimum observed ORRs that would exclude the benchmark ORR with 105 NSCLC subjects and 60 CRC subjects are 32% and 20%, respectively.

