9.5.1 Analyses of Primary Efficacy Endpoint(s)

The number and percentage of subjects with a best overall response of Complete Response (CR), Partial Response (PR), Stable Disease (SD), Progressive Disease (PD), Not Evaluable (NE) will be presented. ORR will be summarized along with a Clopper-Pearson exact 95% confidence interval ([Clopper and Pearson, 1934](#)). Subjects without a post-baseline tumor assessment will be considered non-responders.

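### The phase 2 futility rule predicts a weaker event than the stated ORR objective, so NSCLC continues when that objective is very unlikely; separately, the 30% CRC cut-off lowers power from about 90% to about 85%

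*Supplement*

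**What the plan says.** Protocol 10.2.2 (Amendment 3) sets the phase 2 objective by tumor type as an ORR over a "benchmark rate to exclude based on the lower limit of the 95% CI for the observed ORR for each tumor type". It continues: "The benchmark ORR to exclude is selected as 23% for NSCLC and 10% for CRC". It claims "approximately a 90% probability that the lower limit of the ORR 95% CI exceeds the tumor-specific benchmark ORR" with 105 NSCLC and 60 CRC subjects, and adds: "The minimum observed ORRs that would exclude the benchmark ORR with 105 NSCLC subjects and 60 CRC subjects are 32% and 20%, respectively". SAP 9.5.1 fixes the interval method: "ORR will be summarized along with a Clopper-Pearson exact 95% confidence interval".

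The interim rule in SAP 7.1.3.2 (repeated in protocol 10.4.1.3.2) predicts something else. Go is a posterior probability of at least 80% that the NSCLC ORR exceeds 0.23, or at least 95% that the CRC ORR exceeds 0.10, with a Beta(1,1) prior. "Futility will be met if it is predicted that there is a small probability of reaching a Go Criterion upon full enrollment", and small means below 5% for NSCLC and below 30% for CRC. The SAP adds: "The Go criterion is for interim futility analysis purpose only". The rule is nonbinding and uses site-read responses. NSCLC enrollment is not paused for it. SAP Tables 6 and 7 (protocol Tables 14 and 15) list the boundaries and the cumulative probability of futility.

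**The concern.** A predictive-probability rule answers one question: given the data so far, how likely is the trial to end where it needs to end? Here the end point inside the calculation is not the one in the sample size section. A trial can satisfy Go and still miss its objective. The tables then report how often futility is declared, but not how often the objective is met.

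Two things are at stake. NSCLC subjects may go on being enrolled when the benchmark is unlikely ever to be excluded. The power quoted in protocol 10.2.2 also takes no account of the futility rule, and in CRC the cut-off is six times the NSCLC one.

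**Working it through.** **Inputs.** Benchmarks 0.23 and 0.10, N = 105 and 60 (protocol 10.2.2). Posterior cut-offs 80% and 95%, predictive cut-offs 5% and 30%, Beta(1,1) prior, looks every 10 subjects from 25 (NSCLC) and from 20 (CRC) (SAP 7.1.3.2). Clopper-Pearson 95% interval (SAP 9.5.1). The true ORR behind the 90% is not stated.

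**Thresholds.** Go is the smallest r at which Beta(1+r, 1+N−r) gives enough probability above the benchmark. The objective is the smallest r whose exact lower limit exceeds it.

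| | Go | Lower limit at Go | Objective | Lower limit there | One response fewer |
|---|---|---|---|---|---|
| NSCLC | 28/105 (posterior 0.830; 27 gives 0.767) | 18.5% | 34/105 | 23.6% | 33: 22.7% |
| CRC | 10/60 (posterior 0.962; 9 gives 0.920) | 8.3% | 12/60 | 10.8% | 11: 9.5% |

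34/105 = 32.4% and 12/60 = 20% agree with the minimum ORRs in protocol 10.2.2.

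**Reproducing the plan.** With x responses in n, the predictive probability of reaching target t is P(Y ≥ t − x), where Y is beta-binomial with size N − n and parameters 1 + x and 1 + n − x. Using t = 28 and 10 gives stopping counts of 3, 5, 7, 10, 13, 16, 19, 22 and 2, 3, 5, 7, exactly as in Tables 6 and 7. Cumulative probabilities from an exact recursion agree within about 1 point.

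**NSCLC.** At the smallest count that continues:

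| Responses/n | Predictive probability of Go (28) | Of the objective (34) |
|---|---|---|
| 4/25 | 11.0% | 2.8% |
| 6/35 | 7.9% | 1.2% |
| 8/45 | 5.1% | 0.38% |
| 11/55 | 7.3% | 0.34% |
| 14/65 | 9.2% | 0.22% |
| 17/75 | 10.5% | 0.09% |
| 20/85 | 10.8% | 0.013% |
| 23/95 | 8.5% | 0 (23 + 10 = 33) |

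Now change the target to 34 and the cut-off to 2.5%. The stopping counts become 3, 6, 9, 12, 16, 19, 23, 27.

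| True ORR | Plan: stops by n = 95 / mean N / success | Target 34, below 2.5% |
|---|---|---|
| 23% | 64% / 75 / 1.7% | 92.5% / 58 / 1.7% |
| 30% | 14% / 99 / 32.9% | 46% / 88 / 32.1% |
| 38% | 0.8% / 105 / 90.0% | 4.9% / 103 / 89.3% |

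At ORR 30%, Table 6 shows 23% cumulative futility through 105, yet the objective is missed in 100 − 32.9 = 67.1% of trials.

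**CRC.** Solving P(X ≥ 12 | 60, p) = 0.90 gives p = 26.4%. The chance of at least 12/60 with the rule followed:

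| Target, cut-off | Stopping counts | ORR 25% | ORR 26.4% | Stops at ORR 10% (mean N) |
|---|---|---|---|---|
| No rule | – | 85.2% | 90.0% | – |
| 10, below 30% (plan) | 2, 3, 5, 7 | 79.9% | 85.2% | 91.5% (28.2) |
| 12, below 30% | 2, 4, 6, 8 | 77.1% | 82.8% | 96.1% (25.9) |
| 10, below 5% | 0, 2, 3, 6 | 85.0% | 89.8% | 78.4% (41.7) |
| 12, below 5% | 1, 3, 5, 7 | 83.1% | 88.1% | 90.2% (32.2) |

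At the fixed 30% cut-off, moving the target from 10 to 12 lowers power further. Lowering the cut-off restores it. The loss therefore belongs to the cut-off.

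**The case against.** The best defense is that interim counts are immature. A subject is evaluable with six weeks of response data, scans go on every six weeks, ORR uses best overall response, and the SAP's primary analysis waits for six-month follow-up. Someone with stable disease at a look may respond later. Interim counts are site-read while the primary analysis uses independent review, so they can differ either way, and 105 is a minimum. A target below the final bar could be a sensible margin for all this.

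That stands against one tempting inference from the 23/95 row: that the plan continues NSCLC when success is strictly impossible. It is zero only if interim responses are final and the two reads agree. However, the plan's own predictive model also holds observed counts fixed, and no margin is stated or sized.

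A second tempting inference is that the mismatch costs CRC power. It does not. Go is the easier target, so predicting it stops CRC less often.

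Other points also stand. The rule is nonbinding and its purpose is disclosed. A looser futility target does not inflate type I error (1.8% and 1.5% at the benchmarks from the success rule alone). A stricter NSCLC rule would stop many more trials at ORRs of 28% to 32% (63% versus 24% at 28%), losing precision on response duration, PFS and safety. A sponsor may weigh that. None of this explains the choice of target or tells the reader what the rule does to the chance of success.

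**Conclusion.** Two separate points hold.

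- **NSCLC.** The rule predicts an event six responses short of the stated objective (28 against 34). Trials that just continue have under a 3% predictive chance of meeting the objective at every look, and under 0.5% from 45 subjects on. These figures take interim counts as mature and identically read. Power is barely touched (90.2% without the rule, 90.0% with it, at ORR 38%); the cost is weak stopping at the benchmark.
- **CRC.** If the rule is followed, the 30% cut-off costs about 5 points (90.0% to 85.2% at ORR 26.4%; 85.2% to 79.9% at 25%). The approximately 90% in protocol 10.2.2 is then not delivered. The 26.4% is back-solved, and the loss disappears to the extent that the review team overrides the rule.

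This should be changed before the rule is used. It does not threaten the validity of the primary analysis.

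**What to change.** - **NSCLC:** define the predictive target as at least 34/105 with a low cut-off. Below 2.5% gives the stopping counts shown above. Keeping 5% with that target costs more (power 88.0% at ORR 38%, mean N 51 at ORR 23%).
- **CRC:** either restate power with the futility rule applied, or lower the cut-off. Target 12/60 with below 5% gives about 88% at ORR 26.4%.
- **Tables 6 and 7 (protocol Tables 14 and 15):** recompute them, add the probability of meeting the objective with futility applied, and replace the rows at 105 and 60, which are not interim looks, with the success rule.
- If a margin for late responses or reader differences is intended, state it and its size.

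**Cost.** The SAP, the protocol tables and the review team's charter change; no procedure is added. NSCLC gives up about 0.7 points of power at ORR 38% and stops early more often at ORR 30% (46% against 14%), where success moves only from 32.9% to 32.1%. The mean saving of about 17 NSCLC subjects at ORR 23% is an upper bound, because enrollment is not paused. CRC needs about 4 more subjects on average at ORR 10% (32.2 against 28.2) and stops there 90.2% of the time instead of 91.5%.
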